To evaluate the difference in insulin lispro PK when LY900014 and Humalog are administered as different test bolus doses with an insulin pump to patients with T1DM during a breakfast meal test	AUC, C _{max} , T _{max} , early 50% T _{max} , and late 50% T _{max}
Secondary Objectives	Endpoints
To evaluate the sustainability of any difference in insulin lispro PK of LY900014 and Humalog over 3 days when administered as different test bolus doses with an insulin pump to patients with T1DM during a breakfast meal test	AUC, C _{max} , T _{max} , early 50% T _{max} , and late 50% T _{max}
To evaluate the difference in GD response when LY900014 and Humalog are administered as different test bolus doses with an insulin pump to patients with T1DM during a breakfast meal test	ΔAUC
To compare the durability of GD response over 3 days when LY900014 and Humalog are administered as different test bolus doses with an insulin pump to patients with T1DM during a breakfast meal test	ΔAUC
Exploratory Objectives	Endpoints
To evaluate the safety and tolerability of LY900014 administered with an insulin pump	Adverse events, anti-insulin lispro antibodies, infusion-site reactions/pain, and frequency and/or severity of hypoglycemia
To compare the GD response using CGM when LY900014 and Humalog are administered as different test bolus doses with an insulin pump to patients with T1DM during a standardized lunch meal	ΔAUC
To compare the GD response using CGM when LY900014 and Humalog are administered as different test bolus doses with an insulin pump to patients with T1DM during a standardized dinner meal	ΔAUC
To evaluate the intrasubject and intersubject insulin lispro PK variability of LY900014 compared with Humalog after 3 days of CSII	CV of AUC
To determine catheter occlusion rates with LY900014 and Humalog after 3 days of CSII	Microscopic assessment of infusion tubing after 3 days of use or in case of suspected catheter occlusion
To perform an exploratory comparison of glucose fluctuations with time in patients with euglycemia, hypoglycemia, and hyperglycemia receiving LY900014 and Humalog	CGM profiles during inpatient periods: time in euglycemia, hypoglycemia, and hyperglycemia

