5.1.1.4. Day 3 Activities

Before the start of the run-in period, the cannulation of 2 veins will be performed. On Day 3, approximately 7 hours before dosing (approximately 1:00 AM), the run-in period for the Day 3 MMTT will start. The run-in period, breakfast MMTT, and lunch meal procedures will be performed as described above for the Day 1 procedures.

If a catheter occlusion alarm occurs <5 hours after the start of the MMTT on Day 3, the data will not be used for analysis and the entire period can be repeated a maximum of 1 time. If catheter occlusion occurs >5 hours after the start of the MMTT on Day 3, the data will be used for analysis for the breakfast meal test, but the lunch test meal on Day 3 will be omitted and handled

as missing data, and the patient will have the catheter and CGM system removed. A new catheter will be inserted for use with the patient's own insulin pump.

After the Day 3 lunch meal procedures are completed (approximately 5 hours after the start of the lunch meal), the catheter and CGM system will be removed. A new catheter will be inserted for use with the patient's own insulin pump. However, if the patient plans to stay at the clinic until that evening (approximately 5:00 PM) for Day –1 procedures for the next period, the new catheter and reservoir will not be inserted until after the standardized dinner (at approximately 7:00 PM) is given (Day –1 for the following period).

Additionally, a macroscopic and microscopic check of the removed catheter and catheter tubing will be performed on site, ideally immediately after removing but within 120 minutes to exclude micro-occlusions and/or particles in the tubing.

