5.1.2. Outpatient Procedures

For the time between consecutive periods, patients will continue their CSII therapy with their own pump using Humalog until the evening of Day –1 (after completing the Day –1 standardized dinner) of the next meal test period when they will receive either the LY900014 or Humalog with a CCI [REDACTED], according to their assigned treatment. Patients will be instructed to perform regular blood glucose monitoring consisting of a minimum of daily 4-point self-measured plasma glucose profiles (preprandial for 3 meals [that is, breakfast, lunch, and dinner] and at bedtime) using their own glucose meters. Patients will be instructed to use a diary to document any AEs, hypoglycemic events, meals (time, units of carbohydrate equivalent), insulin bolus doses and basal rate changes, and the self-measured plasma glucose values. The source data for self-measured plasma glucose values will be the patient's diary. Upon return to the CRU on the evening of Day –1, the diary will be reviewed and checked for hypoglycemic events and AEs. The individual insulin doses may be adapted by the investigator for the outpatient period if clinically indicated to prevent significant hyperglycemia or hypoglycemia. Additionally, as determined by the investigator, interim telephone visits may occur at any time during the outpatient periods to review the safety and well-being of the patient.

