	Dinner	SS	SS		RS	RS		SS	SS		RS	RS	
2		Treatment A			Treatment B			Treatment A			Treatment B		
	Breakfast	SS	SS	SS	SS	SS	SS	SD	RS	SD	SD	RS	SD
	Lunch	SD	SD	SD	SD	SD	SD	RD	RD	RD	RD	RD	RD
	Dinner	RS	RS		RS	RS		SS	SS		SS	SS	
3		Treatment B			Treatment A			Treatment B			Treatment A		
	Breakfast	SD	RS	SD	SD	RS	SD	SS	SS	SS	SS	SS	SS
	Lunch	RD	RD	RD	RD	RD	RD	SD	SD	SD	SD	SD	SD
	Dinner	SS	SS		SS	SS		RS	RS		RS	RS	
4		Treatment B			Treatment B			Treatment A			Treatment A		
	Breakfast	SS	SS	SS	SD	RS	SD	SS	SS	SS	SD	RS	SD
	Lunch	SD	SD	SD	RD	RD	RD	SD	SD	SD	RD	RD	RD
	Dinner	RS	RS		SS	SS		RS	RS		SS	SS	

Note: Patients will be randomized to 1 of 4 treatment sequences, each comprising different administration modes for the prandial bolus dose for the breakfast, lunch, and dinner meals on Days 1 through 3 in each of the 4 periods.

“Treatment A” and “Treatment B” may represent either Humalog or LY900014. Patients will be assigned a treatment sequence according to the actual randomization schedule provided to the site.

Bolus dose administration modes: RD = rapid dual-wave; RS = rapid single-wave; SD = standard dual-wave; SS = standard single-wave.

Table 1. Planned Treatment Sequences by Period

Patients will be discharged from the CRU on Day 3 (at least 5 hours after the start of the lunch meal) or later, if deemed necessary for safety monitoring as determined by the investigator. Study treatments may be administered on consecutive days from one period to the next, and a maximum time of 1 week is permitted between consecutive periods.

Patients will continue their individual CSII basal rate using the insulin pump during the entire study including the meal test days unless safety issues arise; in this case, the investigator will discuss a change of the basal rate with the sponsor clinical research physician (CRP) and implement this change, if necessary, to prevent any medical problems. However, during the MMTT (approximately 6:00 AM to 2:00 PM on Days 1 and 3) and the high-glycemic index breakfast meal test (approximately 6:00 AM to 2:00 PM on Day 2), the basal rate will be changed to a single hourly rate based on the patient’s mean basal needs during the meal test period. For all lunch and dinner meals during the inpatient periods, the patients’ individual CSII basal rate will be continued unchanged.

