6. TREATMENTS

The following is a list of the study treatment abbreviations that will be used in the TFLs.

For Safety outputs

Study Treatment Name	Treatment order in TFLs
Humalog	1
LY900014	2
Bolus Dose Administration Method	Method order in TFLs
Standard dual-wave	1
Standard single-wave	2
Rapid single-wave	3
Rapid dual-wave	4

Statistical analysis treatment names

Study Treatment Name	Treatment order in TFL
Humalog standard dual-wave	1
Humalog standard single-wave	2
Humalog rapid dual-wave	3
Humalog rapid single-wave	4
LY900014 standard dual-wave	5
LY900014 standard single-wave	6

LY900014 rapid dual-wave	7
LY900014 rapid single-wave	8

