9.5 Safety and Tolerability Assessments

9.5.1 Adverse events

Where changes in severity are recorded in the Case Report Form (CRF), each separate severity of the adverse event (AE) will be reported in the listings, only the most severe will be used in the summary tables. A pre-existing condition is defined as an AE that starts before the patient has provided written informed consent and is ongoing at consent. A non-treatment emergent AE is defined as an AE which starts after informed consent but prior to dosing. A treatment-emergent AE is defined as an AE which occurs postdose or which is present prior to the first dose and becomes more severe postdose. Any AE that occurs during the outpatient period will be associated with open-label Humalog (and not treatment).

All AEs will be listed. Treatment-emergent AEs will be summarized by treatment, bolus administration mode, meal, severity and relationship to the study drug. The frequency (the number of adverse events, the number of patients experiencing an adverse event and the percentage of patients experiencing an adverse event) of treatment-emergent adverse events will be summarized by treatment, bolus administration mode, meal, Medical Dictionary for Regulatory Activities (MedDRA) version 19.1 system organ class and preferred term. The summary and frequency adverse event tables will be presented for all causalities and those considered related to the study drug. Any serious adverse events will be tabulated.

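### SAP 9.5.1 removes site reactions that first appear after discharge from the by-treatment AE tables of the product infused at that site, for LY900014 and Reference Humalog alike

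*SAP*

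**What the plan says.** SAP 9.5.1 gives the attribution rule for AEs outside the inpatient stays: "Any AE that occurs during the outpatient period will be associated with open-label Humalog (and not treatment"). It sets no time window after catheter removal and makes no exception for the old catheter site or for events judged related.

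The same section states how the tables are built: "Treatment-emergent AEs will be summarized by treatment, bolus administration mode, meal, severity and relationship to the study drug". It adds that "The summary and frequency adverse event tables will be presented for all causalities and those considered related to the study drug", with no separate assignment rule for the related events.

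Protocol 5.1.2 describes the outpatient interval: "For the time between consecutive periods, patients will continue their CSII therapy with their own pump using Humalog". On the gap from one period to the next, SAP Section 5 says "Study treatments may be administered on consecutive days from one period to the next, and a maximum time of 1 week is permitted between consecutive" ones. Under Protocol 5.1.1.4 the study catheter comes out on Day 3, about 5 hours after the start of lunch, and then "A new catheter will be inserted for use with the patient's own insulin pump", unless the patient stays on for the next period.

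Protocol Section 4 (Table ITSC.4.1) lists the endpoints of the exploratory safety objective: "Adverse events, anti-insulin lispro antibodies, infusion-site reactions/pain, and frequency and/or severity of hypoglycemia".

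SAP Section 6 introduces its treatment names with "The following is a list of the study treatment abbreviations that will be used in the TFLs". For safety outputs it names only Humalog and LY900014, and has no entry for open-label Humalog.

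**The concern.** A reaction at a catheter site belongs to what was infused there, whatever the patient is using when it becomes visible. LY900014 contains treprostinil for a local vasodilator effect (Protocol 3.2), and the site receives basal and bolus insulin for about three days. Protocol 3.3 names hypersensitivity and injection-site reactions among the potential risks. A reaction that appears hours or days after removal is a plausible local effect of the inpatient product, and rapid clearance of lispro from the blood does not rule it out.

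The rule assigns such an event by calendar time only. The patient diary is reviewed for AEs at the next admission (Protocol 5.1.2), so the event would be recorded and then left out of the treatment comparison. Protocol 10.3.1.1 promises incidence for each treatment by association as the investigator sees it. For these events the rule overrides that judgement. What is at stake is the completeness of the by-treatment AE tables for a named tolerability endpoint.

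**Working it through.** The plan states no figure for this rule, so there is none to reproduce. The check has three parts.

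**1. Can another planned output recover a post-discharge site reaction under its treatment?**

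- Insertion-site and VAS assessments are scheduled at 0, 20, 40, 60, 120, 180, 240 and 300 minutes after the breakfast bolus on Days 1 to 3 (Protocol Section 2). That is 8 time points per day, the last being 300 minutes after the Day 3 breakfast bolus.
- Lunch starts at least 5 hours after breakfast, and the catheter stays in until about 5 hours after lunch starts. The last scheduled site check therefore comes about 5 hours before removal, and none is scheduled afterwards.
- SAP 9.5.8 and 9.5.9 summarise those assessments by treatment. They keep what is seen with the catheter in place but cannot contain a later reaction.
- A targeted medical review precedes discharge on Day 3. It too comes before the interval in question.

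AE reporting is thus the only route for a site reaction that first appears after discharge, and SAP 9.5.1 sends it to open-label Humalog.

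**2. How many LY900014 periods does the rule reach?**

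The treatment orders in SAP Table 1 are AABB, ABAB, BABA and BBAA. Taking A as LY900014:

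| Sequence | LY900014 periods | What follows each |
|---|---|---|
| 1 (AABB) | 1, 2 | LY900014; Humalog |
| 2 (ABAB) | 1, 3 | Humalog; Humalog |
| 3 (BABA) | 2, 4 | Humalog; follow-up |
| 4 (BBAA) | 3, 4 | LY900014; follow-up |

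Of 8 LY900014 periods, 2 precede another LY900014 period, 4 precede a Humalog period and 2 precede follow-up. Taking B as LY900014 gives the same counts, so they also hold for Humalog periods.

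With 20 completers and 5 per sequence (equal allocation is assumed, as the documents do not state it):

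- LY900014 periods: 20 × 2 = 40
- followed by a between-period interval: 5 × (2 + 4) = 30, and 30/40 = 75%
- followed by follow-up only: 5 × 2 = 10, and 10/40 = 25%

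Thirty is an upper limit, because a patient who stays in the unit between periods has no outpatient interval. For the other 10, the SAP does not say whether the 7 to 14 days of follow-up count as outpatient.

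**3. What could be hidden?**

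The documents give no rate of delayed reactions, so the risks per period below are assumptions. Expected events = 30 × risk, if every interval is spent as an outpatient.

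| Assumed risk, LY900014 / Humalog | Under the SAP rule: LY900014, randomised Humalog, open-label Humalog | By treatment infused at the site: LY900014 vs Humalog |
|---|---|---|
| 2% / 2% | 0, 0, 1.2 | 0.6 vs 0.6 |
| 5% / 2% | 0, 0, 2.1 | 1.5 vs 0.6 |
| 10% / 2% | 0, 0, 3.6 | 3.0 vs 0.6 |
| 20% / 5% | 0, 0, 7.5 | 6.0 vs 1.5 |

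Under the rule both randomised treatments show zero in every row. A difference is hidden only if the true risks differ.

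**The case against.** Assigning an AE to current exposure is a recognisable convention: after discharge the patient is on a new catheter, a personal pump and commercial Humalog. The rule treats both formulations alike. Most information on site reactions comes from the scheduled inpatient assessments, which it does not touch. All AEs are listed, so a delayed reaction stays visible to anyone who reads the listings. Protocol 3.2.1 reports, from preliminary Phase 1b data that include pump use, no significant difference in injection-site tolerability. Safety is exploratory and descriptive, so no primary or secondary conclusion changes.

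All of this stands as a limit on the size of the point. It does not answer the rule itself. The convention suits events remote from the study site, but at a former study site it gives the wrong product, and a listing does not replace a by-treatment table.

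A reader might go further and infer that these reactions are charged to the comparator, tilting the comparison towards LY900014. The documents do not support that. The rule names open-label Humalog and excludes study treatment. Protocol 7.1.1 and 7.1.2 separate investigational Reference Humalog from noninvestigational Humalog. Inflation of the comparator would need open-label events to be printed in the Humalog column. The two-label list in SAP Section 6 leaves that open without saying so, and the table shells are a separate document. Nor do the documents support a percentage by which LY900014 incidence is understated.

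**Conclusion.** The gap is real and narrow. As written, SAP 9.5.1 keeps site reactions that first appear in a between-period outpatient interval out of the AE tables for both randomised treatments, whatever the causality judgement. The certain effect is undercounting under both. A hidden difference between formulations is possible but not shown.

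The reach is at most 30 of 40 LY900014 periods, and likewise 30 of 40 Humalog periods, given 20 completers and equal allocation. The other 10 of each are undefined because the status of follow-up is not stated. The SAP also speaks of events that occur, not events that start, in the outpatient period, so a reaction that begins in the unit and worsens at home is not clearly handled. The number of events affected cannot be derived from the documents. Severity: minor.

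**What to change.** Amend SAP 9.5.1 as follows:

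- Attribute any AE at a study catheter site to the inpatient treatment infused at that site, whenever it starts, including during follow-up.
- Keep other outpatient AEs under open-label Humalog, displayed separately from randomised Humalog, and add that label to SAP Section 6.
- Add one supportive table of outpatient and follow-up AEs by preceding inpatient treatment.
- State how follow-up after Period 4, back-to-back periods, and events that begin in the unit and continue after discharge are assigned.

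I would not reassign non-site AEs by a fixed time window. The documents give no basis for its length, and it would move events that arise on open-label Humalog onto study treatment.

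The cost is SAP wording, one AE flag for former study sites and one extra descriptive table. Study design and the schedule of assessments do not change.

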9.5.2 Concomitant medication

Concomitant medication will be coded using the WHO drug dictionary (Version September 2016). Concomitant medication will be listed.

9.5.3 Clinical laboratory parameters

Clinical chemistry, hematology and urinalysis data outside the reference ranges will be listed.

Values for any clinical chemistry, hematology and urinalysis values outside the reference ranges will be flagged on the individual patient data listings.

9.5.4 Vital signs

Vital signs data will be summarized by treatment and bolus administration mode, together with changes from baseline, where baseline is defined as predose of Day 1. Furthermore, values for individual patients will be listed.

9.5.5 Dosing information

Daily bolus dosing and basal dosing information will be listed.

9.5.6 Immunogenicity

Immunogenicity data will be listed. The number of patients who have detected anti-insulin lispro antibodies at predose and follow-up, and number of patients who have anti-insulin lispro antibodies that become cross-reactive with human insulin at follow-up will be summarized by overall population.

9.5.7 Blood glucose monitoring and Hypoglycemia

Hypoglycemic events will be appropriately recorded in the CRF. In the case of a hypoglycemic event, the actual blood glucose value, if measured, will be recorded in the CRF, together with any treatments administered, and the time of occurrence relative to the patient's last meal. Each category of hypoglycemic events (defined below) will be listed and summarized for the outpatient, inpatient before the MMTT, inpatient during the MMTT, or inpatient after the MMTT periods and overall. Severe hypoglycemic events will be reported as SAEs. "During MMTT" refers to 0-300 minutes postdose. Events will be summarized by treatment, bolus dose administration method and meal.

Hypoglycemia is defined as follows:

- Documented Hypoglycemia:
 - Symptomatic hypoglycemia: An event during which typical symptoms of hypoglycemia are accompanied by plasma glucose ≤ 70 mg/dL (≤ 3.9 mmol/L)
 - Asymptomatic hypoglycemia: An event not accompanied by typical symptoms of hypoglycemia but with plasma glucose ≤ 70 mg/dL (≤ 3.9 mmol/L)
- Unspecified hypoglycemia: An event during which plasma glucose ≤ 70 mg/dL (≤ 3.9 mmol/L) but no information relative to symptoms of hypoglycemia was recorded.
- Probable symptomatic hypoglycemia: An event during which symptoms indicative of hypoglycemia are not accompanied by a plasma glucose determination (but that was presumably caused by PG ≤ 70 mg/dL [≤ 3.9 mmol/L]).
- Severe hypoglycemia: An event requiring assistance of another person to actively administer carbohydrate, glucagon, or other resuscitative actions.

- Nocturnal hypoglycemia: Any hypoglycemic event (documented symptomatic, asymptomatic, probable symptomatic, or severe hypoglycemia) that occurs between bedtime and waking
- Relative hypoglycemia: an event during which typical symptoms of hypoglycemia, that do not require the assistance of another person, are accompanied by plasma glucose >70 mg/dL (3.9 mmol/L), but these levels may be quickly approaching the 70 mg/dL (3.9 mmol/L) threshold
- Total hypoglycemia: an optional category that combines all cases of hypoglycemia. If an event which hypoglycemia falls into multiple subcategories, the event is only counted once in this category
- Overall hypoglycemia: This category combines all cases of hypoglycemia (documented hypoglycemia and probable symptomatic hypoglycemia, including severe hypoglycemia). If an event of hypoglycemia falls into multiple subcategories, then the event is only counted once in this category.
- Serious and clinical important hypoglycemia: A hypoglycemia that is accompanied by a measured plasma glucose <54 mg/dl (<3.0 mmol/L).

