A study using model-predicted optimized bolus delivery has shown that a bolus for a mixed meal containing a substantial amount of fat (approximately 40% of total calories), compared to a meal with the same carbohydrate content but only a minimal amount of fat, needs a larger bolus dose and a dual-wave delivery method to achieve optimal postprandial glucose control (Bell et al. 2016). Therefore, testing a dual-wave bolus dose and different bolus speed options to support a safe and efficient use of LY900014 in T1DM patients using an insulin pump is of great clinical interest.

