Patients who are eligible to participate in the study based on the results of the screening procedures will proceed to a 1-week lead-in period. During the lead-in period, patients will (if not receiving Humalog) switch from their short-acting insulin used before the start of the study to Humalog, which will be administered using their own personal pump. Patients will also be provided with a general diabetes training including, but not limited to, dose calculation for short-acting insulins; correct self-monitoring of plasma glucose; and interpretation of results, symptoms, and treatment of hypoglycemia. A patient diary will also be provided for documentation of dosing, meals, and glucose monitoring outcomes.

Patients will be randomly assigned to a treatment sequence according to the actual randomization schedule provided to the site at the beginning of or during the lead-in period. The Medtronic CCI [REDACTED] will be used for all study treatment administrations, while maintaining the catheter needle at the same catheter insertion-site location for the 3-day duration of each study period. Before each MMTT on Day 1 and Day 3, a run-in period to stabilize plasma glucose levels will occur. Details of run-in activities are described in Section 5.1.1.2 and Section 2 of the protocol. Before the breakfast meal test on Day 2, the patients will have their plasma glucose monitored approximately every hour during the night to ensure that the targeted plasma glucose range is met before the start of the Day 2 meal test.

Note: Patients will be randomized to 1 of 4 treatment sequences; each sequence has 4 periods. Each period comprises dosing with assigned treatment (Humalog or LY900014) over Days 1 to 3.

Figure 1. Study design

Patients will be required to attend the clinical research unit (CRU) on at least 8 occasions:

- a visit for informed consent
- a screening visit (may occur up to 21 days before the lead-in period)
- an initial CRU visit at the start of the 1-week lead-in period in which all patients will receive Humalog as their CSII
- 4 inpatient stays from Day -1 to Day 3 (one in each study period)
- a follow-up visit (within 7 to 14 days after the last dose or early discontinuation)

Treatment Sequence	Meal	Period 1			Period 2			Period 3			Period 4		
		Days			Days			Days			Days		
		1	2	3	1	2	3	1	2	3	1	2	3
1		Treatment A			Treatment A			Treatment B			Treatment B		
	Breakfast	SD	RS	SD	SS	SS	SS	SD	RS	SD	SS	SS	SS
	Lunch	RD	RD	RD	SD	SD	SD	RD	RD	RD	SD	SD	SD

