9.5.9 Pain Measurements using the Visual Analog Scale (VAS)

Pain measurements during bolus application will be assessed using the electronic version of the 100-mm validated VAS (or electronic VAS [eVAS]) for pain. Data will be listed and summarized by treatment and bolus administration mode.

VAS data will also be summarized based on the following categories of score: 0 mm, 1-10 mm, 11-20 mm, 21-30 mm, 31-40 mm, etc. up to the maximum category by treatment and timepoint, and also the categories ≤ 10 mm, ≤ 20 mm and ≤ 45 mm. The table will show number and percent of patients with observations in each category.

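### Breakfast adverse event tables set bolus modes given 1, 2 and 3 times per product side by side with no per-bolus denominator, so modes of equal risk will differ by exposure alone

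*SAP*

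**What the plan says.** SAP 9.5.1 plans two sets of adverse event tables. One is a summary: "Treatment-emergent AEs will be summarized by treatment, bolus administration mode, meal, severity and relationship to the study drug". The other gives frequencies by system organ class and preferred term within the same strata, and its statistics are spelled out: "the number of adverse events, the number of patients experiencing an adverse event and the percentage of patients experiencing an adverse event". No rate per bolus, per test meal or per unit of time is mentioned.

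SAP 9.5.7, on hypoglycemia, says "Events will be summarized by treatment, bolus dose administration method and meal". It also splits events into outpatient, before, during and after the MMTT, but names neither a statistic nor a denominator. SAP 9.5.9, on VAS pain, says "Data will be listed and summarized by treatment and bolus administration mode"; its table of score categories is by treatment and timepoint, not by mode. Dosing data are only listed (SAP 9.5.5). SAP 6 fixes a display order for the four modes in safety outputs, so presentation by mode is clearly intended.

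Exposure follows from SAP Table 1 (SAP 5; the same as Table ITSC.5.1 in the protocol). For Sequence 1 the first two meal rows read "Breakfast SD RS SD SS SS SS SD RS SD SS SS SS" and "Lunch RD RD RD SD SD SD RD RD RD SD SD SD", with two periods on each product.

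**The concern.** A count of events, or of patients with at least one event, rises with the number of boluses at risk. If one breakfast mode is given three times and another once, the first collects more events even when each bolus carries the same risk. A reader who compares rows of the breakfast table would see the rapid single-wave bolus as the safest and the standard single-wave bolus as the least safe, for no reason but the schedule.

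Protocol 3.1 makes such a reading likely, because it gives as a motive "testing a dual-wave bolus dose and different bolus speed options to support a safe and efficient use of LY900014".

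A second problem is separate from exposure. At breakfast the rapid single-wave mode occurs only on Day 2 and the standard dual-wave mode only on Days 1 and 3. Those days differ in meal, catheter age, overnight glucose run-in (Protocol 5.4) and the conditional 30% dose increase, which covers the Day 1 and Day 3 breakfasts but not the Day 2 breakfast (Protocol 5.5). Risk per bolus could differ by day whatever the mode.

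**Working it through.** **The plan's own figure.** The documents give no event rate. The only computed figure is the sample size, used here just for N = 20. With a within-patient CV of 35.9%, the log-scale SD is √ln(1 + 0.359²) = 0.348, SE = 0.348 × √(2/20) = 0.110 and the effect is ln 0.75 = −0.288. At two-sided α = 0.1, the noncentral t with 19 df gives 80.9% power, which agrees with the stated 80%.

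**Exposure.** Counting every cell of Table 1 by product gives the same result in all four sequences (RS rapid single-wave, SD standard dual-wave, SS standard single-wave, RD rapid dual-wave):

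| Meal | Boluses per patient per product |
|---|---|
| Breakfast | RS 1 (Day 2), SD 2 (Days 1, 3), SS 3 (Days 1–3) |
| Lunch | RD 3, SD 3 |
| Dinner | SS 2, RS 2 |

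Only breakfast is unbalanced. For 20 completers it has 20 RS, 40 SD and 60 SS boluses per product.

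**Equal risk per bolus.** Let p be the chance of an event after one breakfast bolus, the same for all modes, with at most one event per bolus. The value of p is an assumption, so a range is shown. With k = 1, 2, 3 boluses:

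- expected events = 20 × k × p
- percentage of patients with an event = 1 − (1 − p)^k, if events are independent

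| p | Expected events RS/SD/SS | % of patients RS/SD/SS | Ratio of % SS:RS |
|---|---|---|---|
| 0.05 | 1/2/3 | 5.0/9.8/14.3 | 2.9 |
| 0.10 | 2/4/6 | 10/19/27.1 | 2.7 |
| 0.20 | 4/8/12 | 20/36/48.8 | 2.4 |
| 0.30 | 6/12/18 | 30/51/65.7 | 2.2 |
| 0.40 | 8/16/24 | 40/64/78.4 | 2.0 |

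**Within-patient correlation.** In a beta-binomial simulation (100,000 runs, 20 patients, p = 0.10) the patient percentages are 10/17.2/22.7 at correlation 0.2 and 10/14.5/17.3 at correlation 0.5. The ordering stays and the SS:RS ratio falls to about 1.7. Expected event counts remain 1:2:3.

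**How often a single table would mislead.** With no true difference and correlation from 0 to 0.5, the SS event count exceeds the RS count in 75–78% of simulated trials at p = 0.05, 91–92% at p = 0.10 and 98–99% at p = 0.20. For the number of patients with an event, the figures are 57–77%, 74–89% and 87–97%.

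**After dividing by boluses given.** All three modes have the same expected rate p. The SS rate exceeds the RS rate in 41–48% of simulated trials (ties count as not exceeding), so the systematic ordering is gone.

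**Matched days.** On Days 1 and 3, SD and SS each have 2 planned breakfast boluses per product; on Day 2, RS and SS each have 1. Exposure is equal, and day and meal type are held fixed.

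**The case against.** The strongest reply is that no safety comparison across modes is planned. Safety is an exploratory objective about LY900014, the tables are descriptive, and the Protocol 3.1 wording is background. This stands as a limit on severity. It does not remove the distortion, because the SAP itself chooses to tabulate by mode.

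Four wider readings are tempting, and the documents do not support them.

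- **Hypoglycemia is certainly affected.** SAP 9.5.7 names no statistic, and the table shells are a separate document not available here; a per-bolus denominator may be in them. The window during the MMTT is also ambiguous. If MMTT means Days 1 and 3 only, as in SAP 9.3.1, that window holds 2 SD and 2 SS breakfasts and no RS, and is balanced. SAP 5 can be read to include Day 2. The point for hypoglycemia is therefore conditional.
- **All by-mode safety tables are affected.** Lunch (3 against 3) and dinner (2 against 2) are balanced. Totals over meals would be unequal, but the adverse event and hypoglycemia tables are split by meal.
- **VAS pain is inflated by exposure.** The mean of a score does not rise with the number of boluses, and the category table is not by mode. Only the confounding with day and meal type applies to VAS.
- **The product comparison is biased.** Within a mode and meal, planned exposure to LY900014 and Humalog is equal.

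It is also fair to say that the distortion holds in expectation: with rare events a single table may not show it. The threefold figure applies to event counts only. Splitting by day will thin cells that come from about 20 completers.

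**Conclusion.** The point holds for the breakfast adverse event tables in SAP 9.5.1. It holds for the breakfast hypoglycemia tables in SAP 9.5.7 only if they use the same statistics. The 1:2:3 exposure is exact under the planned schedule. Its effect is a 1:2:3 ratio in expected event counts and, for p from 0.05 to 0.40 with independent events, a 2.0- to 2.9-fold difference in patient percentages between standard and rapid single-wave, less with within-patient correlation. These sizes rest on equal risk per bolus and on event rates that the documents do not give.

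The confounding of breakfast mode with day and meal type is a second fault. A per-bolus rate does not cure it, and it is the only part that reaches VAS pain by mode. The primary PK inference is not touched. This should be corrected, but it does not threaten the trial's main conclusions.

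**What to change.** In SAP 9.5.1 and 9.5.7, for the breakfast by-mode tables:

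- Show in each cell the number of boluses (test meals) actually given, and report events per bolus and the percentage of test meals with at least one event. Keep patient percentages for the product comparison.
- Use actual rather than planned counts. A Day 2 test can be dropped (Protocol 5.1.1.3), and meal tests or periods can be repeated (Protocol 5.1.1, 5.1.1.2 and 5.1.1.4). State how such breakfasts are counted.
- Present breakfast modes on matched days only: standard dual-wave against standard single-wave on Days 1 and 3, and rapid against standard single-wave on Day 2. Do the same for breakfast VAS by mode in SAP 9.5.9.
- Name the statistic in SAP 9.5.7, and say whether its MMTT window includes Day 2.

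The matched-day layout follows the separation of Days 1 and 3 from Day 2 already used for PK and GD, and the by-day display already planned for injection-site data in SAP 9.5.8. Lunch and dinner tables can stay as they are. No new data are needed; the cost is extra table programming and sparser cells in descriptive tables.
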